11.4.2 Sensitivity Analyses for Primary Endpoint

A sensitivity analysis will be conducted on the primary endpoint to assess a site effect. This sensitivity analysis will be conducted in a similar manner as for the primary endpoint. The model described for the primary endpoint will also include a term for site in the ANOVA model. If the term for site is significant at the 2-sided alpha of 5% then it will be concluded that a site effect exists. Sites having less than 2 subjects in either treatment group will be pooled together into one site.

The primary analysis will also be conducted for the ITT population. There will be two sensitivity analyses using the ITT population, the first will use all ITT subjects and apply a multiple imputation method for missing AHI values. Missing values will be imputed based on baseline

characteristics of sex, age, and baseline AHI value. The second sensitivity analysis will include all ITT subjects with observed data collected.

11.4.3 Secondary Effectiveness Analysis

Mean ODI will be summarized descriptively by treatment group. The population for this secondary analysis is the mITT population.

11.4.4 Safety Analysis

Adverse events will be summarized descriptively by treatment group, system organ class, and preferred term. An additional summary will be provided for device and procedure related adverse events by treatment group, system organ class, preferred term and severity. Any SAEs or UADEs will be individually reported. A listing of all adverse events will be generated.

11.4.5 Subgroup Analysis

Descriptive statistics of the primary endpoint will be provided for the following subgroups using the mITT population:

- Gender (Female, Male)
- BMI (<30, 30-40)
- Investigational Study Site

12 DATA COLLECTION, QUALITY ASSURANCE AND MANAGEMENT

12.1 Source Documents

Source documents include, but are not limited to, hospital records, clinical and office charts, laboratory notes/reports, memorandums, subjects' evaluation checklists, recorded data from automated instruments, copies of transcriptions certified after verification as being accurate copies, and source document worksheets. Investigators are to maintain all source documents as required by the protocol, including subject source document worksheets, supporting medical records, and informed consents. The source documents will be used at the regular monitoring visits to verify information recorded on the eCRF.

12.2 Recording of Data

Data will be recorded electronically on electronic case report forms (eCRFs).

Clinical data generated in the study will be submitted to the Sponsor or its designee for quality assurance review and statistical analysis. Incoming data will be reviewed to identify inconsistent or missing data and Unanticipated Adverse Device Effects. Data queries will be issued to address data issues and will be followed up with calls or emails to the investigational sites and during site visits by site monitors. Quality assurance procedures are designed to ensure that complete, accurate and timely data are submitted, that protocol requirements are followed, and that adverse events and adverse device effects are detected, managed and reported as required.

12.3 Data Processing

Data processing will be performed according to FRESCA's SOPs or those of its delegated vendors, ensuring adherence to GCPs. Audits may be performed for quality assurance of data handling.

13 RISK AND BENEFIT OF THE INVESTIGATIONAL DEVICE

13.1 **Potential Benefits**

There are no direct benefits anticipated to study subjects for participation, other than possible knowledge gained about their current condition during the sleep studies. Indirect benefit to patients with OSA will be gained from the data arising from the study, and the demonstration of potential benefits of the FRESCA Airbox Positive Airway Pressure System.

13.2 Risk Assessment

Limiting device use to three, discreet sleep nights is unlikely to have long-term risk of any kind. Possible short-term risk is limited to undergoing a poor night's rest if the device does not reduce symptoms of sleep disordered breathing. The anticipated adverse events for this study are listed in Section 14 below.

13.3 Risk-Benefit Assessment and Risk Mitigation

Both social benefit and subject-level benefit appear to exceed the risks associated with performing the trial. This favorable risk-benefit profile confirms that it is appropriate to perform this clinical trial to demonstrate the non-inferiority of the FRESCA Airbox System compared to the predicate (control) FRESCA System in the treatment of OSA.

Risk mitigation measures that will be implemented in this trial include:

- Full informed consent.
- Consistent implementation of a well-designed protocol.
- Inclusion and exclusion criteria designed in part to screen out subjects at any elevated risk.
- Selection of well-qualified Investigators and staff.
- Proper training and preparation of investigational sites and personnel.
- Continuous observation of study subjects by clinical staff during device use.

13.4 Non-Significant Risk Determination

The FRESCA Airbox Positive Airway Pressure System described in this protocol does not meet the definition of a significant risk device as defined in 21 CFR 812.3(m), specifically:

• Intended as an implant and presents a potential for serious risk to the health, safety, or welfare of a subject;

- Purported or represented to be for a use in supporting or sustaining human life and presents a potential for serious risk to the health, safety, or welfare of a subject;
- For use of substantial importance in diagnosing, curing, mitigating, or treating disease, or otherwise preventing impairment of human health and presents a potential for serious risk to the health, safety, or welfare of a subject; or
- Otherwise presents a potential for serious risk to the health, safety, or welfare of a subject.

The following information supports a non-significant risk determination for the FRESCA Airbox System:

- There are no invasive procedures involved in the study.
- None of the expected adverse events as defined in the protocol would be life-threatening or would result in any permanent impairment of a body function or permanent damage to a body structure.
- The investigational device is a modification to a Positive Airway Pressure System previously cleared for market by the FDA for the treatment of OSA.
- If the subject feels any discomfort during the study, he/she will be able to remove the device immediately.
- The investigational device will be used during a laboratory-based PSG evaluation monitored by a respiratory technician.

14 ADVERSE EVENTS

14.1 Listing of Possible Adverse Events

Adverse events which might occur or have been known to occur with Positive Airway Pressure treatment include but are not limited to the following:

- Irritations from PSG equipment sensor interfaces
- Skin / nose irritation from the mask
- Facial marks from the mask
- Eye irritation
- Runny or stuffy nose
- Difficulty breathing
- Difficulty sleeping
- Dry mouth
- Nosebleeds
- Headache
- Claustrophobia
- Shortness of breath
- Dizziness
- Tiredness
- Panicky feeling

However, because this is an investigational device, there may be additional risks and discomforts associated with the device that are not known at this time.

Any clinically significant, undesirable experience (sign, symptom, illness, or other medical event) occurring or worsening during the study period should be considered an adverse event. A clinically significant event is any event (sign, symptom, lab/imaging abnormality, or diagnosis) that is noteworthy enough to merit documentation in standard medical records (e.g. History and Physical, Progress notes, clinic visit notes, etc.) or require medical intervention to correct. Events and findings that would otherwise be termed adverse events, but are not new onset or worsening events, will be defined as pre-existing conditions and will not be analyzed as adverse events for this study.

Throughout the course of the proposed study, all efforts will be made to remain alert to possible adverse experiences or untoward findings. Any adverse events, complications, and suspected device deficiencies observed by the investigator or reported by the subjects, whether or not ascribed to the procedure or investigational device, will be recorded in the appropriate section of the subject's case report form. All adverse events will be monitored until adequately resolved or the subject exits from the study.

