7.2 Clinical Testing

A non-inferiority (NI) study was previously completed comparing the FRESCA device patient interface (mask, valve and hose) to a commercially available CPAP device patient interface (mask and hose). The study enrolled subjects diagnosed with obstructive sleep apnea who were compliant users of a commercially-available CPAP mask and hose. This was a prospective, randomized, cross-over multi-site study designed to determine whether treatment with the FRESCA device was non-inferior to treatment with the subject's prescribed CPAP device.

The study met the primary effectiveness endpoint, i.e., the mean AHI and ODI, and confirmed the non-inferiority of the FRESCA device patient interface compared to the CPAP device patient interface in the treatment of OSA. The FRESCA device demonstrated significant improvement in both AHI and ODI (compared to baseline). Most of the device adverse events were asymptomatic or mild and all resolved without the need for any treatment. There were no serious adverse events nor unanticipated adverse device effects. The study results demonstrated the safety and effectiveness of the FRESCA device patient interface.

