10.5 Baseline Evaluation

- 1) Baseline information:
 - a) Patient identifier
 - b) Date of birth
 - c) Gender
 - d) Ethnicity
 - e) Height (inches)
 - f) Weight (pounds)
 - g) BMI (calculated from height and weight)
- 2) Physical Examination:
 - a) Vital signs (HR, BP, Oral temperature)
- 3) Medical history, including but not limited to:
 - a) Cardiovascular disease
 - b) Cancer
 - c) Respiratory disease
 - d) Psychiatric illness
 - e) Prior surgical intervention for OSA
 - f) Non-OSA sleep disorders

¹ Current CPAP users cannot use the same brand and model CPAP mask as they currently use at home.

- g) Severe nasal allergies, sinusitis or nasal blockages
- 4) Listing and dosages of all current prescription medications or other agents that may affect sleep and/or PSG results

10.6 **Detailed Description of Study Procedures**

This study is not blinded, as both the investigator and subject will be aware of the therapy that is being utilized. However, investigators and study staff will minimize discussion about the particular therapy. Since the outcome measures are objective observations of each subject's sleep architecture and respiratory events, and the scoring of the PSGs will be performed by a masked central scorer, bias resulting from the open label nature of this study will be minimized.

Consented subjects who met the inclusion / exclusion criteria and completed a valid PSG titration study will be randomized. Following randomization, subjects are considered enrolled.

Subjects will undergo one in-lab PSG titration study to identify their therapeutic pressure setting. Subjects who complete a valid PSG titration study will be scheduled for two additional sleep nights, preferably two consecutive nights. The number of allowable calendar days between the two randomized sleep nights is 0 - 10 days. These sleep nights will be randomized to one of two sequences.

Sequence 1: Original (predicate) FRESCA device set to PSG-titrated fixed pressure on night 1 / investigational FRESCA Airbox device set to auto-adjusting pressure + EPR on night 2.

Sequence 2: Investigational FRESCA Airbox device set to auto-adjusting pressure + EPR on night 1 / Original (predicate) FRESCA device set to PSG-titrated fixed pressure on night 2.

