14.2 Severity of Adverse Events

The following definitions for rating severity of Adverse Events will be used by Investigators and study monitors:

- Asymptomatic: An adverse event that is not noticed by the subject and does not require additional therapy.
- Mild: An adverse event that is noticeable to the subject and may require additional therapy.
- Moderate: An adverse event that interferes with the subject's activities and requires intervention or additional therapies.
- Severe: An adverse event that is intolerable or incapacitating and necessitates additional therapy or places the subject at immediate risk of harm.

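### Protocol section 14.1 makes clinical significance a condition for an adverse event, which conflicts with the minor events it lists and with the Asymptomatic grade in 14.2

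*Protocol*

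**What the plan says.** Protocol section 14.1 states what counts as an adverse event: "Any clinically significant, undesirable experience (sign, symptom, illness, or other medical event) occurring or worsening during the study period". It then explains clinical significance. An event qualifies if it is "noteworthy enough to merit documentation in standard medical records" or if it needs medical intervention to correct. Either route is enough. The section gives no example of where the line falls and does not name who draws it. Events that are neither new nor worsening are treated as pre-existing and left out of the analysis.

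The same section opens with 15 items, introduced as follows: "Adverse events which might occur or have been known to occur with Positive Airway Pressure treatment include but are not limited to the following". They include facial marks, a runny or stuffy nose, dry mouth and tiredness. A later sentence takes in complications and suspected device deficiencies along with adverse events; those "observed by the investigator or reported by the subjects, whether or not ascribed to the procedure or investigational device, will be recorded".

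Section 14.2 defines the lowest severity grade, Asymptomatic, as "An adverse event that is not noticed by the subject and does not require additional therapy". Section 7.2 reports on the earlier FRESCA study: "Most of the device adverse events were asymptomatic or mild and all resolved without the need for any treatment".

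On blinding, section 10.6 says that "both the investigator and subject will be aware of the therapy that is being utilized". Only the central PSG scorer is masked.

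Protocol section 11.4.4 and SAP section 11.1 summarize adverse events descriptively by treatment group, with no test. Protocol section 11.2 assigns safety to the ITT population, of up to 50 subjects. The SAP has no adverse event definition of its own.

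**The concern.** The definition sets a condition that many of the protocol's own listed events would meet only if someone chose to see them as chart-worthy. The list and the lowest severity grade show that such events are meant to be in scope; the definition lets them fall out. The earlier study's device events were mostly of this kind, so the condition bears on the part of the safety profile where most events can be expected.

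The staff who apply the condition know which device the subject wore, and the result is a table of counts by device in a study meant to support a 510(k) submission. Lost events make both devices look better tolerated than they were. If events are lost at different rates on the two devices, the comparison shifts as well.

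**Working it through.** The documents state no adverse event rate or recording rate, so there is no figure to reproduce. The check sets the passages side by side and then illustrates the size with assumed rates.

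**1. The list against the definition.** Take a mask mark or a dry mouth that clears by itself. It needs no intervention, so it can qualify only by being worth a chart note, and no rule says when it is. One site can record it and another omit it, and both have followed 14.1.

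**2. The lowest grade against the definition.** An Asymptomatic event is by definition unnoticed by the subject and untreated. It too can enter only as chart-worthy. The severity scale therefore provides for events that the definition may already have removed.

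**3. Whether another sentence lifts the condition.** The recording sentence in 14.1 requires adverse events to be recorded whatever their attribution, but it uses the term just defined. Its two additions, complications and suspected device deficiencies, fall outside that term. However, the summaries in protocol 11.4.4 and SAP 11.1 tabulate adverse events. The SAP adds no threshold or definition.

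**4. Whether the defence of the open label covers adverse events.** Section 10.6 rests that defence on objective PSG outcomes and a masked scorer. Neither applies to adverse events. The investigator also judges relatedness to device and procedure (14.3, 14.4), and no masked review of adverse events is described.

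**5. The reference for new or worsening.** The baseline items in 10.5 do not name dry mouth, headache or tiredness, although the history list is open-ended. Under the protocol, screening may be up to 90 days before titration. The items collected on the randomized nights (10.6) do not specify a check of symptoms at the start of the night. When the nights are consecutive, a mark left from night 1 has no specified reference on night 2.

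**6. Size, on assumed rates.** Let p be the true event rate, equal on both devices, and r the probability that an event is recorded.

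- Recorded rate on a device = p × r
- Apparent difference (new minus predicate) = p × (r_new − r_pred)

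| r_new / r_pred | p = 10% | p = 20% | p = 40% |
|---|---|---|---|
| 1.00 / 1.00 | 10 v 10, difference 0 | 20 v 20, difference 0 | 40 v 40, difference 0 |
| 0.50 / 0.50 | 5 v 5, difference 0 | 10 v 10, difference 0 | 20 v 20, difference 0 |
| 0.50 / 0.75 | 5 v 7.5, difference −2.5 | 10 v 15, difference −5 | 20 v 30, difference −10 |
| 0.50 / 1.00 | 5 v 10, difference −5 | 10 v 20, difference −10 | 20 v 40, difference −20 |

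Entries are percentages and percentage points. With 50 subjects on each device and p = 20%, 50 × 0.20 = 10 subjects have an event and 10 × 0.50 = 5 are recorded. Swapping the two recording probabilities reverses the sign. Equal under-recording lowers both rates and leaves the difference at 0.

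**The case against.** The strongest reply is that this is loose drafting and that the text as a whole points towards capture. Being chart-worthy is enough without any intervention. Section 14.1 itself calls the listed items adverse events and tells staff to stay alert for untoward findings. The Asymptomatic and Mild grades would be pointless if minor events were out of scope. Subjects are observed by clinical staff in the laboratory (13.3, 13.4), and an adverse event assessment is scheduled on every PSG night and at exit. The eCRF, which may already prompt for events, is not among the documents.

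Most of this stands as evidence of intent. A reader might infer that 14.1 excludes minor events outright; the documents do not support that. But intent shown elsewhere does not remove a condition written into the definition, and staff who apply it as written may leave listed events out.

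Three further points stand:

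- **Skew is not shown.** A reader might infer that the table is biased between devices, or favours the new one. That would need recording to differ by device. The documents give no evidence of it, and in this crossover the same rule applies to both devices.
- **The earlier study's definition is not given.** Section 7.2 is only a summary, so one cannot conclude that the two studies' counts are not comparable.
- **A reference for earlier symptoms is not wholly absent.** Medical history is an open list that names nasal problems, SAP section 9.4 lists conditions with dates and ongoing status, and adverse events are assessed on the titration night. What is missing is a specified check at the start of each night.

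Nor is the adverse event table all that is reported beyond AHI and ODI: the SAP also summarizes other PSG measures (10.5) and device malfunctions (Tables 14.2.6 and 14.2.7).

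**Conclusion.** The definition in 14.1 conflicts with the list in the same section and with the lowest grade in 14.2, and nothing else in the protocol or SAP resolves the conflict. Read literally, it lets device-aware staff leave out listed minor events. The descriptive by-device counts can therefore be too low, in proportion to the share not recorded: half recorded means half the true rate. A distorted comparison is a possibility that depends on recording that differs by device or site. In the illustration that distortion runs from 2.5 to 20 points, but those rates are assumed and the sign could go either way.

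The primary AHI analysis and its non-inferiority conclusion are unaffected. The point is still worth correcting, because the change is small and events not recorded on the night cannot reliably be recovered later.

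**What to change.** In protocol section 14.1, define an adverse event as any undesirable sign, symptom, illness or other medical event that is new or worsening during the study period, including the listed events, whether or not it is clinically significant. Keep the study period as the time frame. A definition tied only to change after lights-off would lose events at mask fitting and between nights.

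Record clinical significance and need for intervention as attributes of each event, not as a condition for entering it.

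At the assessments already scheduled on the titration night and both randomized nights, ask about the 15 listed events in identical wording for both devices. Note symptoms already present at the start of each night, so that new or worsening has a reference.

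The cost is a change of protocol wording and a short checklist at existing assessments. The planned summaries in protocol 11.4.4 and SAP 11.1 can stay as they are. The downside is that more mild events will appear in the tables.

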9 STUDY DESIGN

9.1 General

[figure not shown]
This study is focused on evaluating the efficacy of the FRESCA Airbox Positive Airway Pressure System in subjects with diagnosed obstructive sleep apnea who meet the inclusion and exclusion criteria established in this protocol. Up to fifty (50) subjects will be enrolled at up to six (6) study sites.

The device will be evaluated using polysomnography results and requires each subject's participation in 3 overnight in-lab sleep nights. See Figure 2 and Table 1.

Subjects will undergo one in-lab PSG titration study to identify their therapeutic pressure setting. Subjects who complete a valid PSG titration study that achieves a therapeutic pressure setting (i.e., AHI < 10/hr) will be scheduled for two additional sleep nights, preferably two consecutive nights. The number of allowable calendar days between the two randomized sleep nights is 0 - 10 days. These sleep nights will be randomized to one of two sequences.

Sequence 1: Original (predicate FRESCA device) set to fixed-pressure on night 1 / FRESCA Airbox device set to auto-adjusting pressure + EPR on night 2

Sequence 2: FRESCA Airbox device set to auto-adjusting pressure + EPR on night 1 / Original (predicate FRESCA device) set to fixed-pressure on night 2

assessment and exits the study

Fig. 2: Study Flow Diagram

Visit	Screening Visit ≤90 days prior to PSG Titration Night	PSG Titration Night	Night 1	Night 2	Study Exit Visit ¹
Informed Consent	Х				
Medical History	Х				
OSA History	Х				
Weight measure	Х				
Height measure	Х				
BMI	Х				
Vital Signs	Х				
Inclusion/Exclusion Review	X				
Confirm eligibility	Х	Х			
Schedule study nights	Х				
Medication Review	Х	Х	Х	Х	
Randomization			Х		
PSG Procedure		Х	Х	Х	
Sleep Scoring		Х	Х	X	
Adverse Events		Х	Х	X	Х

Table 1: Schedule of Visits and Procedures

¹ Study exit visit can be performed at the conclusion of the final sleep night.

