If the subject fails to have a valid PSG Study on either night, the subject is considered an early study exit and excluded from the mITT analysis of the primary effectiveness endpoint. These subjects will be analyzed and summarized separately, including the reason(s) they did not complete a valid PSG study.

The following data will be collected for the PSG titration study night and PSG randomized sleep nights 1 and 2:

PSG Titration Study

- 1) Date of PSG Titration
- 2) Brand and model of PSG equipment
- 3) Mask style used during titration
- 4) Brand and model of CPAP flow generator
- 5) Brand and model of CPAP mask used²
- 6) Total test time (min)
- 7) Total sleep time (min)

² Current CPAP users cannot use the same brand and model CPAP mask as they currently use at home.

- 8) AHI (overall)/h
 9) ODI (overall)/h
 10) Sleep efficiency %
 11) Arousal index ((overall)/h
 12) Minimum sleep SpO₂ %
 13) Mean sleep SpO₂ %
 14) Wakefulness (min)
 15) Stage N1 (min)
 16) Stage N2 (min)
 17) Stage N3 (min)
 18) REM (min)
 19) Prescribed pressure setting (cmH₂O)
- 20) Adverse event assessment

PSG Sleep Nights 1 and 2

- 1) Date of sleep night
- 2) Brand and model of PSG equipment
- 3) FRESCA mask type (nasal pillow or nasal mask)
- 4) Device type (predicate or investigational)
- 5) Device mode (PAP, Auto-adjusting pressure)
- 6) Fixed pressure (if PAP mode)
- 7) Auto-adjusting pressure range (if auto-adjusting pressure mode)
- 8) EPR setting
- 9) Lights off (24-hr. clock)
- 10) Lights on (24-hr. clock)
- 11) Duration of sleep ≥ 4 hrs (Yes or No)
- 12) Sleep night notes (i.e., in-room adjustments, equipment technical issues)
- 13) Medication changes since prior PSG night
- 14) Adverse event assessment

PSG Central Scoring of Sleep Nights 1 and 2

- 1) Date EDF File was Scored
- 2) Date of Sleep Night
- 3) Sleep Night Number
- 4) Total test time (min)
- 5) Total sleep time (min)
- 6) AHI (overall)/h
- 7) ODI (overall)/h
- 8) Sleep efficiency %
- 9) Arousal index ((overall)/h
- 10) Minimum sleep SpO₂ %
- 11) Mean sleep SpO₂ %
- 12) Wakefulness (min)
- 13) Stage N1 (min)
- 14) Stage N2 (min)

15) Stage N3 (min)16) REM (min)17) Comments/notes

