11.2 Analysis Populations

The enrolled population will include all subjects who sign the informed consent document, meet all inclusion and exclusion criteria, complete a valid PSG titration study that identifies a therapeutic pressure setting (i.e., AHI < 10/hr). and have a successful FRESCA mask fit.

The intent-to-treat (ITT) population will include all subjects who are considered enrolled and randomized. The ITT population will be used to determine any adverse event outcomes and assess study safety outcomes.

The modified intent-to-treat (mITT) population will include all intent-to-treat subjects who complete a valid PSG Study during randomized sleep nights 1 and 2. The mITT population will be used to assess study effectiveness outcomes.

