14.3 Relationship of Adverse Event to the Study Device

The relationship of the adverse event to the device will be determined by the Investigator based on his or her clinical judgment and the following definitions:

Definitely Not Related: An adverse event for which sufficient information exists to determine that it is unrelated to device use.

Unlikely Related: An adverse event that occurs during or after device use that could also have been produced by the subject's clinical state or by other therapies. The Investigator determines that the adverse event is unlikely to have been related to the device.

Likely Related: An adverse event that occurs during or after device use that could also have been produced by the subject's clinical state or by other therapies. The Investigator determines that the adverse event is likely to have been related to the device.

Definitely Related: An adverse event that occurs during or after device use and is known to be a complication of the device for which no other reasonable explanation can be determined.

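### Adverse-event follow-up may end on the morning after Night 2, so delayed events and the outcomes of open events can be missed after the last device used

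*Protocol*

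**What the plan says.** - **When monitoring ends.** Protocol Section 14.1: "All adverse events will be monitored until adequately resolved or the subject exits from the study". That sentence makes no exception for SAEs or UADEs.
- **When exit may occur.** Protocol Section 9.1, Table 1, footnote 1: "Study exit visit can be performed at the conclusion of the final sleep night". Table 1 in SAP Section 4.3 carries the same footnote.
- **Spacing of the nights.** Protocol Section 9.1: "The number of allowable calendar days between the two randomized sleep nights is 0 - 10 days". Subjects with a valid titration night "will be scheduled for two additional sleep nights, preferably two consecutive nights".
- **When events are assessed.** Table 1 marks adverse events at the titration night, Night 1, Night 2 and exit. Protocol Section 10.6 includes an adverse event assessment in the lists introduced by "The following data will be collected for the PSG titration study night and PSG randomized sleep nights 1 and 2".
- **What can count as device related.** Protocol Section 14.3 defines the strongest category as "An adverse event that occurs during or after device use and is known to be a complication of the device", with no other reasonable explanation. The two middle categories also extend past the end of use. No length of time is given.
- **How events are reported.** Protocol Section 11.4.4: "Adverse events will be summarized descriptively by treatment group, system organ class, and preferred term". Section 11.2 names the population: "The ITT population will be used to determine any adverse event outcomes and assess study safety outcomes". SAP Section 11.1 plans the same summary. Neither document says which device an event belongs to if it starts between the nights or after Night 2.

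**The concern.** The relatedness definitions intend events after use to count, but the stopping rule and the exit footnote together allow the time after the second device to go unobserved. Several events that Section 14.1 itself lists, such as headache, tiredness, skin or nose irritation, a stuffy nose and nosebleeds, could plausibly begin or persist after the mask comes off.

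Two things are at stake. First, delayed events after the last device night can be missed, which would lower the observed event counts in the by-device summaries that accompany a 510(k) submission (Protocol Section 6.1). Second, an event still open at exit may have no recorded outcome. Protocol Section 7.2 cites, as evidence from the previous study, that the device events all resolved without treatment. This study might be unable to say the same.

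**Working it through.** The plan gives no event rate and no follow-up length, so there is no stated figure to reproduce. The 85% power concerns AHI and does not enter.

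1. **Shortest observation after the second device.** Monitoring ends at exit (Protocol 14.1), and the earliest exit is the end of Night 2 (Table 1, footnote 1). The permitted minimum after use is 0 hours in every schedule.

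2. **Time after the first device that the Night 2 visit can cover.** The documents give no length for a lab night; assume 8 hours. With g full calendar days between the nights, the time from the end of Night 1 to the start of Night 2 is 24 × (g + 1) − 8 hours.
   - Consecutive nights, g = 0: 24 − 8 = 16 hours.
   - Longest gap, g = 10: 264 − 8 = 256 hours. If the ten days are read as a difference in dates, 240 − 8 = 232 hours.

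   No contact is scheduled in this interval. It is time on which the subject can report at Night 2.

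3. **Share of device nights affected.** Each completing subject has two device nights and one of them is the last: 1/2.

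4. **Balance between devices.** SAP Section 4.2 specifies 1:1 allocation in blocks of 4, and SAP Section 12.1 refers to one central list. For 50 subjects, 50 = 12 × 4 + 2. Twelve full blocks give 24 per sequence, and the last two subjects may fall in the same sequence, so the worst split is 26 v 24, or 52% v 48%. Each device is used last about equally often.

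5. **Effect on event rates.** Suppose a share p of a device's events is first noticed after the subject leaves the lab, every subject exits on the last morning, and all such events after Night 1 are captured. The relative loss for each device is then p × 1/2. An assumed p of 20% gives 10%, and 40% gives 20%. The documents contain nothing from which p could be taken, so this shows the form of the loss and does not estimate it.

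6. **Events open at exit, and serious events.** Section 14.1 requires every observed or reported event to be recorded, so the event and its count are kept and only its later course is lost. The SAE definition in Section 14.5 includes hospitalization and persistent impairment, which may not be apparent on the morning of exit. The 24-hour SAE rule in Section 14.5 applies to events during the study. The UADE clock in Section 20.7 starts when the investigator learns of the effect, and Section 21.3 obliges the sponsor to investigate SAEs and UADEs. None of these sets a follow-up period for the subject or plans a contact through which a later event would become known.

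7. **Early exits.** Section 10.6 treats an invalid PSG on either night as an early exit. A subject who leaves after Night 1 has no assured Night 2 assessment, so the first device can also lack follow-up.

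**The case against.** The case against giving this much weight is reasonable. The study involves one supervised night per device, and Section 13.4 classes it as non-significant risk. Exit on the last morning is allowed and not required. Night 2 has overnight observation and an event assessment, with another at exit. Section 14.1 counts only clinically significant events, so some mild next-day complaints would not qualify. Safety summaries are descriptive, and the sole stated objective is non-inferiority. All of this stands and limits the weight of the point, but it does not supply the missing observation.

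A reader might also infer more than the documents support:

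- *That open events are dropped from the analysis.* They are not. Recorded events remain in the case report form, the ITT summaries and the listing.
- *That the second device never gets follow-up, or that reported rates are necessarily too low.* Zero is the permitted minimum, and under-counting depends on how many subjects exit that morning and how many events are delayed.
- *That the first device is observed for up to ten days.* Ten days is the extreme. Consecutive nights are preferred, which leaves under a day, and no contact is scheduled between visits.
- *That one device is favoured.* The imbalance is between periods, and the allocation nearly cancels it between devices.

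**Conclusion.** The concern holds as a gap in safety capture. As written, the plan permits no observation after the second device and requires no outcome for events open at exit. For subjects who complete both nights, one device night in two is exposed to this. Delayed events can be under-captured for both devices to about the same degree. The size of any under-count cannot be derived from the documents, because the share of delayed events and the share of same-morning exits are both unknown.

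The near-equal effect on the devices rests on the 1:1 blocked allocation being largely preserved among subjects who reach Night 2. The primary analysis and sample size are unaffected. This is a cheap improvement, not a flaw that threatens the trial's main conclusion.

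**What to change.** 1. **Protocol Section 14.1.** State that adverse events unresolved at exit, and all SAEs and UADEs, are followed to resolution or stabilization whether or not the subject has exited.
2. **Table 1, protocol and SAP.** Add one telephone adverse-event contact shortly after Night 2 for every subject, and after the last device night for early exits. The sponsor sets the interval. The in-person exit can stay on the last morning.
3. **SAP Section 11.1.** In the by-device tables, count onset in a window of equal length after each device night, assign those events to the device just used, and list later events separately. The window should be no longer than the shortest gap between nights, and the telephone contact must fall late enough to cover it. A rule of 24 hours or the start of the next device night, whichever is first, would not be equal: on consecutive nights with an assumed 8-hour lab night, the first device would get about 16 hours and the second 24.

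The cost is a change of wording, one short call by existing site staff for at most 50 subjects, and a last-subject-out date a few days later. Reported event rates may rise slightly.
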